**Table 3: Data analysis plan**

Objective	Data Analysis
1. Determine the seroprevalence of Cytomegalovirus infection (CMV) in HIV infected and uninfected pregnant women attending CHBAH	Table of maternal demographic and clinical characteristics as proportions
	Maternal CMV seroprevalence expressed as a percentage stratified by HIV status (95% confidence interval)
	Chi square test to compare reactivations/recurrent infections determined by IgG avidity and IgM presence compared to latent infection stratified by HIV status
2. Compare the prevalence of and risk factors for congenital CMV infection in HIV exposed and unexposed newborns	Prevalence of congenital CMV infection in HIV exposed and unexposed infants expressed as a percentage with 95% confidence interval
	Multiple regression analysis to adjust for potential confounders: gender, gestational age at birth, birth weight, birth order, symptoms at birth
	In HIV exposed infants, chi square tests for association between: 

- Congenital CMV infection and maternal ART use

- Congenital CMV infection and severity of maternal immunosuppression (CD4+ count levels)

To explore the association between maternal CMV shedding in vaginal fluid and breast milk and the risk of congenital CMV infection assessed by quantitative CMV PCR.	Chi square test for association between vaginal CMV shedding and congenital CMV infection 

- Stratify by varying ranges of viral shedding (high, moderate, low – quantification to be determined)

- Stratify by HIV infection though will have low power for this

**Potential challenges:** Objective 1, 2 and 5: Mothers may be reluctant to be enrolled in a study for an infection which is unknown to them. To mitigate this, a patient information leaflet will be provided to improve understanding and includes the potential benefit to the infant should he/she

be diagnosed to have congenital CMV ([Appendix 7](#)). Training of researchers in effective communication will be conducted.

Objective 5: CMV viral shedding is cyclical, highest during primary infection; reactivation or reinfection which when occurs during pregnancy may be transmitted to the foetus. This study may be limited by the collection of samples after delivery at which point, viral shedding may have ceased since pregnancy.

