## 2.2 Exploratory objectives

5. To explore the association between maternal CMV shedding in vaginal fluid and breast milk and the risk of congenital CMV infection assessed by quantitative CMV PCR.
6. Determine the incidence of postnatal CMV acquisition, in infants not CMV infected at birth, and explore possible risk factors, including maternal HIV status and the magnitude of maternal CMV shedding in vaginal fluid and breast milk.
7. Explore differences in immune responses to the primary and booster series of vaccinations (DTaP-Hib/HepB, PCV rotavirus and measles vaccines) between congenital CMV cases, postnatally acquired CMV cases and non-CMV infected controls at 6, 12 and 13 months of age.

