**Figure 1: Data collection process for Objectives 1, 2 and 5**

All children with any clinical finding are referred to the neonatology department at CHBAH for clinical management as per standard of care. If a newborn PCR indicates CMV infection, the mother will be contacted telephonically to return to the site within two weeks of birth. At this visit the implications of the positive CMV result will be explained and additional consent for the continued follow up of the child (refer to [Appendix 7](#) for ICF and [Appendix 8](#) for schedule of study visits). Should consent be confirmed, a second saliva swab and a urine sample will be collected for PCR to confirm CMV infection. Babies that test CMV negative on both the second saliva swab and urine will not be enrolled as a case as the saliva positivity may be a result of CMV infected breast milk contamination. However, they will be referred for hearing screening as standard of care. Cases testing positive on both saliva and urine or urine alone will continue as cases for objective 3.

Mothers of CMV cases will have a vaginal swab and breast milk collected for quantitative PCR by a research nurse or the investigator. A subset of mothers that tested seropositive for CMV but gave birth to CMV uninfected neonates will also be recalled as controls for the case mothers in a

1:1 ratio, matched by HIV infection, for vaginal fluid and breast milk collection within 2 weeks of delivery.

**Sample size:** Objective 1: Assuming the estimated CMV prevalence is 86% in pregnant women 200 mothers will be needed to estimate the true value with a desired precision of 5% and confidence interval of 95%.

Objective 2: Prevalence of congenital CMV in HIV exposed neonates is 2.9% and in unexposed neonates is 1.0%. Thus, a total sample of 1662 neonates with 831 HIV exposed and 831 unexposed (1:1 ratio) for 80% power, are required to detect a 2.9 fold difference in CMV prevalence between the 2 groups. This will be increased to 2160 neonates, to accommodate objective 3, to determine clinical sequelae in CMV infected infants ([section 3.3.1, Sample size](#)). After adjusting for 10% being non-evaluable, 1077 HIV exposed (providing 31 CMV infected) and 1077 HIV unexposed infants (providing ~11 CMV cases) are required. Ranges of sample size estimates for varying CMV prevalences by HIV exposure are given in [Appendix 9](#).

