Objective 5: The number of case mothers tested will be determined by the total number of CMV infected neonates that are identified during screening estimated at 42. HIV infection and age matched control mothers will be allocated in a 1: 1 ratio giving a total sample size of 84.

**Laboratory testing:** Maternal blood and vaginal swabs, newborn saliva and urine collected will be stored at -70 °C until processed for CMV serology (IgG and IgM in blood) and DNA by PCR assays (vaginal fluid, saliva, urine) at the RMPRU Laboratory or other collaborating laboratory in South Africa. The turnover time for PCR testing is expected to be within 5 working days of sample collection. Refer to Appendix 10 for laboratory methods of sample processing.

**Data Analysis:** Table 3 describes the planned data analyses, per objective. All analyses will be done on STATA/IC version 13 for Windows, Texas, USA, in consultation with a biostatistician.

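### Exploratory Objective 5 matches control mothers on HIV, but its planned chi-square gives no odds ratio that respects the matching (minor)

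*Combined protocol and SAP*

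**What the plan says.** Section 2.2 lists the aim as exploratory: "To explore the association between maternal CMV shedding in vaginal fluid and breast milk and the risk of congenital CMV infection".

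Section 3.3 gives the design. The data-collection text under Figure 1 recalls CMV-seropositive mothers of uninfected newborns as controls in a "1:1 ratio, matched by HIV infection, for vaginal fluid and breast milk collection within 2 weeks of delivery". The sample-size paragraph for Objective 5 states the rule differently: "HIV infection and age matched control mothers will be allocated in a 1: 1 ratio giving a total sample size of 84". Neither place says whether matching is by individual pair or by frequency.

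The analysis is in the shedding row of Table 3 in section 3.3 (the protocol has a second Table 3, in section 3.4). It names a "Chi square test for association between vaginal CMV shedding and congenital CMV infection" and two sub-items. One divides shedding into high, moderate and low, with "quantification to be determined". The other reads "Stratify by HIV infection though will have low power for this". The row names no odds ratio, confidence interval, pooled stratified test, or conditional or adjusted model. The multiple regression in the same table belongs to Objective 2, and the correlations in section 3.4 belong to the vaccine responses.

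Breast milk is in the objective and is collected: "Mothers of CMV cases will have a vaginal swab and breast milk collected for quantitative PCR". The row has no analysis line for it, and the laboratory paragraph lists "DNA by PCR assays (vaginal fluid, saliva, urine" without it. Appendix 3 (summary of data analysis) and Appendix 10 (laboratory methods) are cited but are not in the text available for review.

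**The concern.** Matching controls on HIV forces cases and controls to have the same HIV mix. If HIV is also related to shedding, the two groups become more alike in shedding than the true association implies. An analysis that ignores the matching factor then gives an odds ratio that is too close to 1. The same applies to age if age is matched and related to shedding. If the matching factor is unrelated to shedding, there is no bias.

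The plan's remaining route is separate HIV strata. The HIV-uninfected stratum has about 11 cases and 11 controls and says little alone. The matching therefore costs effort in selecting controls, but the named analysis does not use it in one summary estimate.

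At stake is the planned result of an exploratory objective: a possibly understated association with no stated interval. The open cut-points and the absent breast-milk line add two smaller gaps in the same row.

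**Working it through.** **Inputs from section 3.3.** 1077 HIV-exposed and 1077 HIV-unexposed newborns; congenital CMV prevalence 2.9% and 1.0%; one control mother per case mother.

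**The plan's own figure.** 1077 × 0.029 = 31.2 and 1077 × 0.010 = 10.8, together 42.0 cases. With 1:1 controls, 42 × 2 = 84 mothers. Both stated figures reproduce, and matching on HIV gives strata of 31 v 31 and 11 v 11.

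**Assumed inputs.** The documents give no shedding rates. Let p₁ and p₀ be the shedding proportions in HIV-infected and HIV-uninfected control mothers, with a true odds ratio of 3 in both strata. A case mother's shedding probability is then f(p) = 3p / (1 − p + 3p).

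**Unstratified odds ratio.** Expected shedders are A = 31 f(p₁) + 11 f(p₀) among 42 cases and C = 31 p₁ + 11 p₀ among 42 controls. The odds ratio is A(42 − C) / [(42 − A)C].

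At 50%/10%: f(0.5) = 0.75 and f(0.1) = 0.25. A = 23.25 + 2.75 = 26.0 and C = 15.5 + 1.1 = 16.6. The odds ratio is 26.0 × 25.4 / (16.0 × 16.6) = 660.4 / 265.6 = 2.49.

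The Mantel-Haenszel estimate from the same expected counts is 3.00 in every row. Power is at two-sided 5%, from 20,000 simulated studies per row.

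| Assumed p₁/p₀ | Unstratified OR | Power, unstratified chi-square | Power, Mantel-Haenszel over HIV |
|---|---|---|---|
| 40%/40% | 3.00 | 0.73 | 0.69 |
| 30%/20% | 2.96 | 0.70 | 0.69 |
| 40%/20% | 2.87 | 0.70 | 0.69 |
| 50%/10% | 2.49 | 0.59 | 0.61 |
| 60%/5% | 2.12 | 0.42 | 0.53 |

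At 40%/30% the unstratified odds ratio is 2.97. With no true association the unstratified chi-square rejects in about 3% to 6% of simulated studies across these settings, so the test is not anti-conservative.

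**The smaller stratum.** With 11 v 11, Fisher's exact test has power of 0.01 to 0.13 for an odds ratio of 3 over the same five settings.

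**Viral load as a quantity.** Assume a 0.75 log₁₀ shift between cases and controls, SD 1.2, 40% of controls detectable, and undetectable values tied at the lowest rank. With no HIV effect on load, the unstratified rank test has power 0.72 and the HIV-stratified one 0.71. If HIV raises load by 1.5 log₁₀, the figures are 0.61 and 0.68. Stratifying the rank test costs almost nothing in the first case and helps in the second.

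The effect of age was not quantified.

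**The case against.** The strongest reply is about weight. The objective is exploratory, its size follows from the number of cases found and not from a power target, and the plan itself admits low power by HIV. Material bias needs a large difference in shedding by HIV status. At 40%/20% the odds ratio is only about 4% low (2.87 / 3 = 0.96), and pooling over HIV has slightly lower power in three of the five settings. The plan's silence on combining strata does not rule it out, and section 3.3 promises analysis in consultation with a biostatistician. All of this stands. It limits the severity but does not supply the missing estimate.

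Three stronger readings are tempting and are not supported.

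- A reader might infer that the plan will run an unordered chi-square across the three load bands and lose power. Table 3 attaches its test to vaginal shedding and lists the bands as a stratification beneath it. How the bands would be tested is not stated.
- A reader might infer that open cut-points mean cut-points chosen for the best p-value. Nothing says so. Simulated false-positive rates for such a search run from about 14% to 32%, depending on the search rule assumed, so they measure that assumption and not this plan.
- A reader might infer that breast milk will go untested or unanalysed. It is to be collected for quantitative PCR, and Appendices 3 and 10 may cover both its analysis and its assay. What can be said is that the main text has no analysis line for it.

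The two matching statements can also be read as one elaborating the other. They still need to be made the same, because the right analysis depends on which rule applies.

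**Conclusion.** The point holds as a minor improvement to an exploratory analysis. Controls are matched at least on HIV, and the main text names no estimate that respects this. Under assumed shedding rates and a common odds ratio of 3 at the 31:11 mix, the unstratified odds ratio is understated by between nothing (equal rates) and about 29% (2.12 at 60%/5%; 1 − 2.12/3 = 0.29). Type I error of a preset test is not inflated. Pooling over HIV clearly gains power only when HIV strongly predicts shedding. No primary conclusion changes, and the quantitative results could be re-analysed later. The conclusion is limited to the main text, since Appendices 3 and 10 could not be checked.

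**What to change.** 1. Make the two matching statements in section 3.3 agree (HIV, or HIV and age), and say whether matching is by pair or by frequency.
2. Name as the main Objective 5 result one odds ratio with a 95% confidence interval. If frequency matched, use Mantel-Haenszel over HIV, or logistic regression adjusted for HIV and age where age is also matched. If pair matched, use conditional logistic regression. Keep the HIV-specific tables as description.
3. Analyse quantitative load with a rank test stratified by HIV, with undetectable values tied at the lowest rank. If high, moderate and low bands are also shown, use a trend test and fix the cut-points before load is linked to case status. Mothers are recalled because case status is known, so it is the linkage that can be delayed.
4. Apply the same analysis to breast milk in Table 3, or cite Appendix 3 if it is already there.

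The cost is wording. Both specimens are already to be collected, so no recruitment or sampling is added. There are two downsides: a slight loss of power if HIV is unrelated to shedding (0.69 against 0.73 at 40%/40%), and the loss of pairs with a missing sample from a conditional analysis.

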### 1.1 Biology and Immunology of CMV

Human CMV is a DNA virus of the Herpesviridae family and viral transmission occurs through body fluids (blood, saliva, breast milk, vaginal fluid, semen and urine) spreading to multiple organs (kidney, liver, lung, brain). CMV demonstrates strain diversity and mixed infection with multiple strains in an individual is common, whilst immunity to CMV is strain specific.

Following primary infection, the virus establishes lifelong persistence and is usually asymptomatic in the immunocompetent. Secondary infection occurs with reactivation of a latent virus or infection with a new strain in a previously CMV seropositive person. Strain specific antibodies (IgM and IgG) and a broad T cell response is activated, limiting viral replication and preventing disease, although unable to completely eliminate the virus.

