Data on congenital CMV infection among HIV exposed infants in sub-Saharan Africa are limited. A Kenyan study of infants born to mothers on perinatal Zidovudine, identified congenital CMV rates of 29% (4/14) in HIV-infected infants and 2.7% (1/37) in HIV exposed but uninfected infants. Zambian newborns admitted to a referral neonatal unit had a congenital CMV prevalence of 3.8% (15/395) whilst prevalence in HIV exposed newborns was 11.4% (9/79). Although HIV prevalence in South African pregnant women is one of the highest in the world (29.9%), a single study has evaluated the relationship between congenital CMV and HIV exposure. In Cape Town, Manicklal et al (2013) found a congenital CMV prevalence of 2.9% (22) in 748 HIV exposed babies. Maternal CD4+ count <200 cells/µL was independently

associated with congenital CMV. Clinical outcomes in these infants and prevalence of congenital CMV among HIV unexposed newborns were not investigated.

**Perinatal and Postnatal CMV infection:** Perinatal CMV infection is defined as CMV infection after 22 completed weeks (154 days) of gestation and seven completed days after birth. Postnatal CMV acquisition is CMV infection acquired any time after birth through consumption of breast milk from CMV seropositive, lactating mothers is common. Most term infants with perinatal CMV infection are asymptomatic, as maternally transferred CMV IgG antibody provides adequate protection against disease. However, studies have identified a significant risk for low-birth-weight (LBW), premature infants for the development of CMV disease such as pneumonia, hepatitis or sepsis-like illness. Data on severity and incidence of disease and long term impact in these infants is currently lacking requiring further study.

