**Table 2: Maternal and newborn data of interest**

Maternal data	Newborn data
Demographic: age, race, and contact details	Demographic: date of birth, gender, race
Clinical data: antenatal care details, past obstetric history, parity, gestation at delivery, delivery details, co-morbidities, HIV status and CD4 count, ART use	Clinical: gestational age at birth, birthweight, head circumference, APGAR scores, HIV exposure, symptoms at birth, discharge or admission details

Newborn saliva samples will be collected by placing an Orocot swab in the mouth for at least 1 minute. All symptomatic neonates for congenital CMV infection ([Appendix 11](#)) will also be screened for other congenital infections which include syphilis, toxoplasmosis, rubella and herpes as is the standard of care at CHBAH.

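### Objective 5 matches on HIV status but leaves CD4 count and ART out of the shedding analysis, so part of any association in HIV-infected mothers could reflect immunosuppression

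*Combined protocol and SAP*

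**What the plan says.** **Matching.** The methods text of section 3.3 recalls seropositive mothers of uninfected newborns as 1:1 controls, "matched by HIV infection, for vaginal fluid and breast milk collection within 2 weeks of delivery". The sample-size text for Objective 5 says: "HIV infection and age matched control mothers will be allocated in a 1: 1 ratio giving a total sample size of 84". The two differ on whether age is a matching factor.

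**Analysis.** The Objective 5 row of Table 3 in section 3.3 gives a "Chi square test for association between vaginal CMV shedding and congenital CMV infection". Its only refinements are strata by shedding level (cut-points still to be set) and "Stratify by HIV infection though will have low power for this". No covariate is named.

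**What is known about immune status.** Table 2 lists "co-morbidities, HIV status and CD4 count, ART use" among the maternal data. Section 1.2 reports that "Maternal CD4+ count <200" cells/µL was independently associated with congenital CMV in a South African cohort of HIV-exposed babies. It also reports that vertical CMV transmission in HIV-infected women fell after ART was introduced in pregnancy. Section 1.1 says that with infection "a broad T cell response is activated, limiting viral replication and preventing disease".

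**Where CD4 and ART are used.** Table 3 uses them only under Objective 2, in chi-square tests against congenital CMV among HIV-exposed infants. Neither is set against shedding.

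**Stated limitation.** For Objective 5 the plan raises sampling after delivery. It does not raise confounding by immune status.

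**The concern.** Matching on HIV yes/no balances infection status, not its severity. Among HIV-infected mothers, the plan's own background implies that low CD4 should be commoner in case mothers than in controls. If low CD4 also increases vaginal shedding, CD4 is a common cause of exposure and outcome. The planned test would then show an association between shedding and congenital infection even where shedding plays no part. ART raises the same question, because the plan links it to transmission too.

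At stake is interpretation. The objective is worded in terms of the risk of congenital infection, and most of the pairs are HIV-infected. As planned, a positive result could not be told apart from a marker of more advanced immunosuppression, although the plan collects the variables needed to look.

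**Working it through.** **1. Plan's own figures (section 3.3, Sample size).**
- HIV-exposed cases: 1077 × 0.029 = 31.2.
- HIV-unexposed cases: 1077 × 0.010 = 10.8.
- Total 42.0. With 1:1 controls, 42 × 2 = 84, as stated.
- HIV-infected share of pairs: 31/42 = 74%. The issue is confined to these pairs.

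**2. Which links the documents supply.**
- CD4 and ART to congenital CMV: stated in section 1.2.
- CD4 to vaginal shedding: not stated. Section 1.1 supports it only indirectly, through T-cell control of replication.
- ART to vaginal shedding: not stated.

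**3. Illustration with no true shedding effect.** The inputs below are assumptions, not document figures. Let q be the share of HIV-infected control mothers with CD4 below 200, a the odds ratio of low CD4 for congenital CMV, and s1 and s0 the shedding prevalence below and above 200. HIV-uninfected mothers shed at s0.

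Formulas: odds of low CD4 in cases = a × q/(1 − q), giving qc = odds/(1 + odds). Shedding in HIV-infected cases = qc·s1 + (1 − qc)·s0, and in HIV-infected controls = q·s1 + (1 − q)·s0. Overall prevalence = (31 × HIV-infected value + 11 × s0)/42.

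*Lower of the strong scenarios: q = 0.25, a = 2, s1/s0 = 60%/30%.*
- qc = 0.667/1.667 = 0.40.
- HIV-infected: cases 0.40 × 0.60 + 0.60 × 0.30 = 42.0%; controls 0.25 × 0.60 + 0.75 × 0.30 = 37.5%. Odds ratio 1.21.
- All pairs: (31 × 0.420 + 11 × 0.30)/42 = 38.9% v (31 × 0.375 + 11 × 0.30)/42 = 35.5%. Odds ratio 1.15.

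*Upper strong scenario: q = 0.25, a = 4, s1/s0 = 70%/20%.*
- qc = 1.333/2.333 = 0.571.
- HIV-infected: 48.6% v 32.5%. Odds ratio 1.96.
- All pairs: 41.1% v 29.2%. Odds ratio 1.69.

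*Weak link: q = 0.25, a = 2, CD4–shedding odds ratio 2, s0 = 30% (so s1 = 46.2%).*
- HIV-infected: 36.5% v 34.0%. Odds ratio 1.11.
- All pairs: 34.8% v 33.0%. Odds ratio 1.08.

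*No link: s1 = s0.* Odds ratio 1.00 throughout.

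The strong scenarios imply a CD4–shedding odds ratio of (0.6/0.4)/(0.3/0.7) = 3.5 up to (0.7/0.3)/(0.2/0.8) = 9.3. A separate grid (q 10–30%, a 2–3, CD4–shedding odds ratio 1–5, s0 30%) gives 1.00 to 1.50 in HIV-infected mothers and 1.00 to 1.36 over all 84.

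**4. Effect on the test.** Simulating 31 HIV-infected and 11 HIV-uninfected pairs with an uncorrected two-sided 5% chi-square, rejection is about 6.6% in the lower strong scenario, 21% in the upper, under 6% with the weak link and 5% with none.

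**5. What an adjusted analysis can carry.** The expected number of shedding-discordant pairs is 31 × [pc(1 − p0) + p0(1 − pc)] + 11 × 2·s0(1 − s0), where pc and p0 are the HIV-infected case and control prevalences.
- Lower strong scenario: 31 × 0.480 + 11 × 0.42 = 14.9 + 4.6 = 19.5.
- Upper strong scenario: 31 × 0.495 + 11 × 0.32 = 15.3 + 3.5 = 18.9.

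Only about 15 of these pairs are HIV-infected, where CD4 and ART matter. That supports one extra term, perhaps two.

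**The case against.** **The CD4–shedding link is an inference.** This stands. Section 1.1 speaks of T-cell responses in general and mentions neither HIV, CD4 nor vaginal fluid. A reader might infer that part of any shedding association *would* be an immunosuppression effect, or that a positive finding could be produced wholly by it. The documents do not support either reading. Without the link the bias is nil. Even the largest spurious odds ratio above falls short of what significance needs: with 13/42 control mothers shedding, roughly 22/42 case mothers must shed (odds ratio 2.45, z = 1.99), so chance would have to add to the bias.

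**In each HIV-infected pair the case mother probably has the lower CD4.** This too is tempting and goes too far. With 25% low CD4 in controls, the case alone is in the low band in 0.40 × 0.75 = 30% of pairs at an odds ratio of 2, and 0.571 × 0.75 = 43% at 4.

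**The objective is exploratory and claims association, not cause.** This is fair, and a marker of immunosuppression can still predict. It limits the weight of the point and is a reason to report the unadjusted estimate as well. It does not remove the ambiguity in a result framed as risk of congenital infection.

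**Shedding may lie on the path from low CD4 to transmission, so adjustment removes signal.** This does not hold. CD4 lies upstream of shedding; adjusting for it closes the back-door path and leaves any effect of shedding on infection open.

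**The plan partly covers it.** Objective 2 would show whether CD4 and ART differ by congenital CMV status, but that neither relates them to shedding nor adjusts the shedding estimate. Section 3.2 refers to a summary of methods and analysis in Appendix 3, which was not in the text available, so the omission is confirmed for the body only.

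**The sample is too small.** This partly stands and shapes the fix: a model with several terms would be fragile.

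**Conclusion.** The point holds as a possible bias in an exploratory objective. The body of the plan leaves CD4 and ART out of the matching, stratification and adjustment for Objective 5, although it collects both and links both to congenital CMV. This affects about 31 of 42 pairs.

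Whether bias follows depends on low CD4 raising vaginal shedding, which is plausible but not stated. On assumed inputs the spurious odds ratio over all 84 mothers runs from 1.0 to about 1.7, with the upper end needing a CD4–shedding odds ratio above 9. The calculation treats CD4 as two levels and gives no figure for ART, for which the documents offer no basis. No primary conclusion is touched; what changes is how a positive shedding result may be read.

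**What to change.** In the Objective 5 row of Table 3 (section 3.3), add an exploratory regression that accounts for the matching. Report the shedding odds ratio without, and then with, one term for maternal CD4 (for example below 200 or not) among HIV-infected mothers. Add ART use only if the data allow. Name a sparse-data method, such as exact or penalised estimation, for use if discordant pairs are few. Add residual confounding by immune status to the stated limitations for Objective 5, and reconcile the two descriptions of the matching factors.

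Matching controls on CD4 band is not recommended. Controls must already be CMV-seropositive, matched on HIV (and age, by the sample-size text), and sampled within 2 weeks of delivery, which narrows the usable pool.

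**Cost.** One line in the table and one sentence of limitation, using variables already listed in Table 2. The adjusted interval will be wider and may be unstable with about 19 discordant pairs. CD4 and ART come from interview and hospital notes, and the plan does not state the timing or completeness of CD4, so the number of mothers with usable values should be reported beside the estimate.
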